6 STUDY TREATMENT

Study drug is defined as any investigational intervention(s), non-investigational product(s), marketed product(s), placebo, or medical device(s) intended to be administered to a study patient according to the study protocol.

Refer to the Pharmacy Instructions for more detailed information regarding the storage, preparation, destruction, and administration of each treatment.

6.1 Study Drug(s) Administered

6.1.1 Investigational Products

Table 7 Investigational Products: NL-201 and Pembrolizumab

Intervention Name	NL-201	Pembrolizumab (Parts 3 and 4 only)
Type	Biologic	
Dose Formulation	Solution for infusion	Solution for infusion
Unit Dose Strength(s)		100 mg/vial
Dosage Level(s)	See Table 8 and Table 9	200 mg Q3W
Route of Administration	IV infusion	IV infusion
Dosing Instructions	NL-201 will be dosed as per the Pharmacy Instructions. IV dosing will occur either every 21 days (for Schedule A) or on Days 1 and 8 of every 21-day cycle (for Schedule B). For IV: patients that weigh ≥ 100 kg, the dose is capped as to not allow more than 100 times the current dose level to be administered to a patient at 1 time (see Table 8 and Table 9). Parts 3 and 4 only: NL-201 to be administered 30-60 minutes post administration of pembrolizumab.	Pembrolizumab will be administered using IV infusion on Day 1 of each 21-day cycle after all procedures and assessments have been completed. Pembrolizumab will be administered as a dose of 200 mg using a 30-minute IV infusion. Sites should make every effort to target infusion timing to be as close to 30 minutes as possible. However, given the variability of infusion pumps from site to site, a window between -5 minutes and +10 minutes is permitted (ie, infusion time is 30 minutes (-5 min/+10 min). After Cycle 1 trial treatment of pembrolizumab may be administered up to 3 days before or after the scheduled Day 1 of each cycle due to administrative reasons, however, pembrolizumab must always be administered on the same day as NL-201 when used in combination. The Pharmacy Manual contains specific instructions for the preparation of the pembrolizumab infusion and administration of infusion solution.
Hospitalization Guidance	Patients will remain in a hospital setting for the first 24 hours after completion of their first dose (IV) on study (may be extended per Investigator discretion), and for 8 hours after receiving subsequent doses. This period of hospital observation will be reduced to 2 hours for patients that have tolerated 3 consecutive doses. Required monitoring times may be adjusted by Neoleukin and/or per DMC recommendation pending review of safety data. Patients should also be advised to stay within a reasonable distance of the clinical site for the first week after the first dose.	
Use	Investigational	
Sourcing	Provided centrally by the Sponsor.	
Packaging and Labeling	Study drug will be provided in glass vials. Each glass vial will be labeled as required per country requirement.	

DMC = Data Monitoring Committee; IV = intravenous; Q3W = every 3 weeks

NOTE: Refer to the Pharmacy Instructions for further details.

NL-201 will be administered until unacceptable toxicity, disease progression, withdrawal of consent, patient or physician decision, or study termination. Patients with progressive disease who have experienced clinical benefit from NL-201 will have the option to continue on therapy past progression.

6.1.1.1 Treatment Beyond Disease Progression

Because of the possibility of an initial increase in tumor burden caused by immune cell infiltration in the setting of a T-cell response (termed pseudoprogression), radiographic progression per RECIST 1.1 may not be indicative of true disease progression. The iRECIST criteria allows for continued treatment beyond apparent progression of disease in order to confirm response. In patients who have initial evidence of radiological disease progression per RECIST 1.1, it is at the discretion of the treating physician whether to continue a patient on study treatment until repeat imaging is obtained. This clinical judgement decision should be based on the patient's overall clinical condition, including performance status, clinical symptoms, and laboratory data. Patient may receive study treatment while waiting for confirmation of disease progression if they are clinically stable as defined by the following:

- Evidence of clinical benefit as assessed by the Investigator (without any rapid disease progression)
- Tolerance of NL-201
- No decline in ECOG performance status that can be attributed to disease progression
- Absence of tumor progression at critical anatomical sites (eg, leptomeningeal disease) that cannot be managed by protocol-allowed medical interventions
- Treatment beyond progression will not delay an imminent intervention to prevent serious complications of disease progression (eg, no evidence that disease progression may result in impending organ impairment)

When feasible, patient should not be discontinued until progression is confirmed. This allowance to continue treatment despite initial radiologic progression takes into account the observation that some patients can have a transient tumor flare in the first few months after the start of immunotherapy, but with subsequent disease response. Patients that are deemed clinically unstable are not required to have repeat imaging for confirmation of disease progression.

Patients who continue treatment beyond radiographic disease progression per RECIST 1.1 should be closely monitored clinically and with a follow-up scan in 4 weeks or sooner at the Investigator's discretion. Treatment should be discontinued if clinical deterioration due to disease progression occurs at any time, or if persistent disease growth is confirmed in a follow-up scan. In addition, patients should be discontinued for unacceptable toxicity or for any other signs or symptoms of deterioration attributed to disease progression as determined by the Investigator after an integrated assessment of radiographic data and clinical status.

6.1.2 Preparation/Handling/Storage/Accountability

- The Investigator or designee must confirm appropriate temperature conditions have been maintained during transit and storage for all study drug received and any discrepancies are reported and resolved before use of the study drug.
- Only patients enrolled in the study may receive study drug and only authorized site staff may supply or administer study drug. All study drug must be stored in a secure, environmentally controlled, and monitored (manual or automated) area in accordance with the labeled storage conditions with access limited to the Investigator and authorized site staff.
- The same lot should be used intra-patient.
- The Investigator, institution, or the head of the medical institution (where applicable) is responsible for study drug accountability, reconciliation, and record maintenance (ie, receipt, reconciliation, and final disposition records).
- Further guidance and information for the final disposition of unused study drugs are provided in the Pharmacy Instructions.

6.1.3 Other Protocol-Required Intervention

To mitigate potential NL-201-related, cytokine associated toxicities, pre-treatment is required to be administered before the start of each NL-201 dose for:

- NL-201 IV doses ≥ 0.6 $\mu\text{g}/\text{kg}$ monotherapy,
- NL-201 doses in combination with pembrolizumab

Required Pre-Medication Protocol for NL-201:

- 1) Pre-medication Requirement: Administration of an agent from each of the following two therapeutic classes must have been completed within 30 to 60 minutes before the start of NL-201 administration:
 - a) Anti-pyretic agent (325-1000 mg acetaminophen [or equivalent]) and to follow NL-201 administration with ongoing anti-pyretic as needed to control fever.
 - b) Histamine receptor antagonist (50-100 mg diphenhydramine [or equivalent]).

The specific drugs discussed above should be selected according to the institutional guidelines. Cases where a patient has a medical condition that precludes pretreatment should be discussed with the Medical Monitor.

- Hydration Requirement: Unless medically contraindicated, infusion of at least 1 liter of normal saline completed on the day of each NL-201 dose administration.
 - a) It is recommended that patients be instructed to orally hydrate with at least 1 liter of appropriate fluids per day for at least 2 days after each NL-201 dose.
- Patients should hold all antihypertensive medications for 12 to 48 hours prior to the administration of NL-201 unless medically contraindicated.

Although continued pre-medication is recommended for all NL-201 administrations, after Cycle 2, the investigator may adjust the dosage and/or avoid using certain pre-medication agents during the treatment, if supported by the investigator's assessment of the risk from cytokine release syndrome, capillary leak syndrome or other infusion-related reactions.

Pre-medication is also permitted if a patient experiences signs or symptoms of cytokine release syndrome, capillary leak syndrome or other infusion-related reaction at lower doses. The DMC may recommend further exploration with additional toxicity mitigations, such as steroids.

For patients that require pre-treatment with antihistamine and/or IV fluids for pembrolizumab, dosing of antihistamine should not be repeated before NL-201 and IV fluids should only be given prior to pembrolizumab, but as close to the start of pembrolizumab infusion as possible.

6.1.4 Cytokine Release Syndrome Management Guidance

In the event symptoms of cytokine release syndrome occur, (fever, chills, nausea, vomiting and hypotension), despite pre-treatment, consider non-steroidal anti-inflammatory drugs (NSAIDs), repeat acetaminophen treatment, and repeat anti-pyretic or histamine receptor antagonist treatment. IVF boluses should also be considered to support symptomatic hypotension.

For symptoms of cytokine release syndrome (including hypotension and hypoxia) that persists and is unresponsive to above treatment, corticosteroid treatment with short biological half-life as per guidance in [Table 11](#) should be considered. Additionally, vasopressor support and/or tocilizumab per institutional guidelines should be considered.

6.1.5 Excluded Treatments, Medical Devices, and/or Procedures During Study Period

The following treatments and/or procedures are excluded during the treatment period of the study:

- Antineoplastic systemic chemotherapy or biological therapy
- Immunotherapy not specified in the protocol
- Chemotherapy not specified in this protocol
- Investigational agents other than NL-201
- Radiation therapy with the following exceptions:
 - Radiation therapy to a symptomatic, non-target lesion or to the brain may be considered after consultation with the Sponsor and medical monitor approval
 - The patient must have clear measurable disease outside of the radiated field
- Live or live-attenuated vaccines (Note: Killed vaccines are allowed.)
- Systemic immunosuppressive therapy, with the following exceptions will be allowed:
 - Stable replacement doses of prednisone \leq 10 mg/day [or equivalent]
 - Stress dosing treatment of patients with adrenal insufficiency
 - Study drug pre-medications for prophylaxis of study drug-related toxicities

- For treatment of any AE (see Table 11 for guidance), provided that the steroid dose is tapered to ≤ 10 mg/day prednisone (or equivalent) prior to receiving the next dose of NL-201
- Any other investigational agent, vaccine, or device
- Any major surgery, unless approved by Medical Monitor

If the Investigator determines that a participant requires any of the aforementioned treatments for any reason, study intervention (NL-201 and for Parts 3 and 4, pembrolizumab) must be discontinued.

6.2 Dose Modification

6.2.1 Dose-Cohort Study Escalation, De-Escalation, and Stopping Rules

6.2.1.1 Part 1: Dose Escalation Study of NL-201 Monotherapy

In Part 1, an mTPI²⁵ will be used to guide dose escalation and de-escalation within each schedule (ie, IV Schedule A, IV Schedule B), with the final decision regarding dose assignment being made by the DMC. In IV Schedule A, patients will be dosed every 21 days, while in IV Schedule B patients will be dosed on Days 1 and 8 of every 21-day cycle. The mTPI design matrix is shown in Figure 5.

Figure 5 mTPI Design Matrix for Part 1

Number of DLT	Number of enrollment at current dose level													
	2	3	4	5	6	7	8	9	10	11	12	13	14	15
0	E	E	E	E	E	E	E	E	E	E	E	E	E	E
1	S	S	S	S	E	E	E	E	E	E	E	E	E	E
2	DU	D	S	S	S	S	S	S	E	E	E	E	E	E
3		DU	DU	D	S	S	S	S	S	S	S	S	S	E
4			DU	DU	DU	D	S	S	S	S	S	S	S	S
5				DU	DU	DU	DU	D	S	S	S	S	S	S
6					DU	DU	DU	DU	DU	D	S	S	S	S
7						DU	DU	DU	DU	DU	DU	D	S	S
8							DU	DU	DU	DU	DU	DU	DU	DU
9								DU	DU	DU	DU	DU	DU	DU
10									DU	DU	DU	DU	DU	DU
11										DU	DU	DU	DU	DU
12											DU	DU	DU	DU
13												DU	DU	DU
14													DU	DU
15														DU

D = De-escalate to the next lower dose; DLT = dose-limiting toxicity; DU = current dose is unacceptably toxic;
 E = Escalate to the next higher dose; mTPI = modified toxicity probability interval; S = stay at the current dose
 Target toxicity rate = 33%
 Flat noninformative prior Beta (1,1) is used as a prior and $\varepsilon_1 = \varepsilon_2 = 0.05$

Assessment of toxicity and dose escalations or de-escalation as guided per the mTPI will be made on an ongoing basis based upon DLT-evaluable patients as defined by occurrence of DLT or completion of 21 days on study, and after review by the DMC. If dose escalation is indicated per mTPI, the DMC will recommend escalation to the next planned dose or additional dose based on review of observed toxicity. Dose escalation and de-escalation will occur independently for each schedule. Intrasubject dose escalation to the next highest dose will be permitted once that dose level is cleared by the DMC in cases where doses have been tolerated by the patient and with Medical Monitor approval (see Table 8 for a proposed dose escalation scheme).

Table 8 Sample Dose Escalation Scheme for Part 1 IV

Monotherapy Cohorts (21-day cycles)		NL-201 dose level ($\mu\text{g}/\text{kg}$)	Maximum dose that may be administered at 1 time (μg) ^a
Schedule A (D1)	Schedule B (D1+D8)		
Planned NL-201 Dose Levels^b			
1A	1B	0.1	10
2A	2B	0.3	30
3A	3B	1.0	100
4A	4B	3.0	300
5A	5B	6.0	600
6A	6B	12.0	1200
Potential NL-201 Intermediate Dose Levels^b			
2A-1	2B-1	0.6	60
3A-1	3B-1	1.5	150
3A-2	3B-2	2.0	200
4A-1	4B-1	4.0	400
4A-2	4B-2	5.0	500
5A-1	5B-1	7.5	750
5A-2	5B-2	9.0	900
5A-3	5B-3	10.0	1000

D = day; DMC = Data Monitoring Committee; IV = intravenous.

a Applicable to patients that weigh ≥ 100 kg (dose is capped as to not allow > 100 times the current dose level to be administered to a patient at 1 time).

b At the recommendation of the DMC or based on Sponsor's determination, additional dose levels may be tested and/or cohorts may be expanded.

The maximum tolerated dose (MTD) is defined as the highest dose for which the probability of a patient experiencing a DLT with NL-201 during Cycle 1 is $\leq 33\%$. At the discretion of the DMC, and in keeping with the pre-specified mTPI design matrix, additional dose levels may be tested to determine the MTD.

Based on review of DLTs, the DMC may initiate step-dosing to improve the tolerability of NL-201, wherein 1 or more step-doses below the target dose would be provided prior to reaching the target dose (see Section 6.2.1.4). If step-dosing is used, the DLT window would extend from the first dose to 21 days after receiving the target dose (ie, would include the initial reduced-dose cycles in addition to the first target-dose cycle). Once a patient receives the intended target dose for their cohort, subsequent doses for that patient will continue at that dose level unless a delay in dosing of > 6 weeks causes washout of the drug, in which case the step-dosing regimen would be repeated if the patient is to resume dosing.

Supported by the mTPI design, the DMC will determine the RP2D and treatment schedule (IV Schedule A, IV Schedule B) for Part 2 by considering the PK, PDn, tolerability, antitumor activity, and the occurrence of any cumulative toxicities over multiple cycles of NL-201.

6.2.1.2 Part 3: Dose Escalation Study of NL-201 in Combination with Pembrolizumab

In Part 3, an mTPI²⁵ will be used to guide dose escalation and de-escalation for NL-201 within each schedule, with the final decision regarding dose assignment being made by the DMC. In Schedule A, patients will be dosed every 21 days, while in Schedule B patients will be dosed on Days 1 and 8 of every 21day cycle. The mTPI design matrix is shown in Figure 6.

Figure 6 mTPI Design Matrix for Part 3

Number of DLT	Number of enrollment at current dose level													
	2	3	4	5	6	7	8	9	10	11	12	13	14	15
0	E	E	E	E	E	E	E	E	E	E	E	E	E	E
1	S	S	S	S	E	E	E	E	E	E	E	E	E	E
2	DU	D	S	S	S	S	S	S	S	E	E	E	E	E
3		DU	DU	D	S	S	S	S	S	S	S	S	S	S
4			DU	DU	DU	D	D	S	S	S	S	S	S	S
5				DU	DU	DU	DU	DU	D	S	S	S	S	S
6					DU	DU	DU	DU	DU	DU	D	S	S	S
7						DU	DU	DU	DU	DU	DU	DU	D	D
8							DU	DU	DU	DU	DU	DU	DU	DU
9								DU	DU	DU	DU	DU	DU	DU
10									DU	DU	DU	DU	DU	DU
11										DU	DU	DU	DU	DU
12											DU	DU	DU	DU
13												DU	DU	DU
14													DU	DU
15														DU

D = De-escalate to the next lower dose; DLT = dose limiting toxicity; DU = current dose is unacceptably toxic;
 E = Escalate to the next higher dose; mTPI = modified toxicity probability interval; S = stay at the current dose
 Target toxicity rate = 30%
 Flat noninformative prior Beta (1,1) is used as a prior and $\varepsilon_1 = \varepsilon_2 = 0.03$

Assessment of toxicity and dose escalations or de-escalation as guided per the mTPI will be made on an ongoing basis based upon DLT-evaluable patients as defined by occurrence of DLT or completion of 21 days on study, and after review by the DMC. If dose escalation is indicated per mTPI, the DMC will recommend escalation to the next planned dose or to an intermediate dose based on review of observed toxicity. Dose escalation and de-escalation will occur independently for Schedules A and B, and a given dose level must be determined by the DMC to be safe on Schedule A prior to enrolling on Schedule B. Dose levels will be escalated more gradually at higher dose levels (see [Table 9](#) for a proposed dose escalation scheme).

Table 9 Sample Dose Escalation Scheme for Part 3

Combination Cohorts (21-day cycles)				Maximum dose of NL-201 that may be administered at 1 time (μg) ^a
Schedule A (D1)	Schedule B (D1+D8)	Pembrolizumab (D1)	NL-201 dose level ($\mu\text{g}/\text{kg}$)	
Planned NL-201 Dose Level				
P-1A	P-1B	200 mg	0.3	30
P-2A	P-2B	200 mg	1	100
P-3A	P-3B	200 mg	3	300
P-4A	P-4B	200 mg	6	600
P-5A	P-5B	200 mg	12	1200
Potential NL-201 Intermediate Dose Level^b				
P-2A-1	P-2B-1	200 mg	0.6	60
P-3A-1	P-3B-1	200 mg	1.5	150
P-3A-2	P-3B-2	200 mg	2.0	200
P-4A-1	P-4B-1	200 mg	4.0	400
P-4A-2	P-4B-2	200 mg	5.0	500
P-5A-1	P-5B-1	200 mg	7.5	750
P-5A-2	P-5B-2	200 mg	9.0	900
P-5A-3	P-5B-3	200 mg	10.0	1000

D = day; DMC = Data Monitoring Committee

- a Applicable to patients that weigh ≥ 100 kg (dose is capped as to not allow > 100 times the current dose level to be administered to a patient at 1 time)
- b At the recommendation of the DMC or based on Sponsor's determination, additional dose levels may be tested and/or cohorts may be expanded.

The MTD is defined as the highest dose for which the probability of a patient experiencing a DLT with NL-201 during Cycle 1 is $\leq 33\%$. At the discretion of the DMC, and in keeping with the pre-specified mTPI design matrix, additional dose levels may be tested to determine the RP2D (see [Table 9](#)).

Based on review of DLTs, the DMC may initiate step-dosing to improve the tolerability of NL-201, wherein 1 or more step-doses below the target dose would be provided prior to reaching the target dose (see [Section 6.2.1.4](#)). If step-dosing is used, the DLT window would extend from the first dose to 21 days after receiving the target dose (ie, would include the initial reduced-dose cycles in addition to the first target-dose cycle). Once a patient receives the intended target dose for their cohort, subsequent doses for that patient will continue at that dose level unless a delay in dosing of > 6 weeks causes washout of the drug, in which case the step-dosing regimen would be repeated if the patient is to resume dosing.

Supported by the mTPI design, the DMC will determine the RP2D for NL-201 in combination with pembrolizumab and treatment schedule (either A or B) for Part 4 by considering the PK, PDn, and any cumulative toxicities over multiple cycles of NL-201 in combination with pembrolizumab.

6.2.1.3 Dose-Limiting Toxicity

Part 1

DLT must occur within Cycle 1 (< 21 days from first dose), or prior to completion of 21 days after first administration of NL-201 or after reaching the cohort target dose (CTD) in patients receiving step-dosing (see Appendix 1 [[Section 10.1](#)]). DLT is defined by the following:

- Any death not clearly due to the underlying disease or extraneous causes
- Hy's law:
 - AST/ALT > 3 × ULN, and
 - TBL > 2 × ULN, and
 - Alkaline phosphatase < 2 × ULN without alternative etiology
 - No other reason can be found to explain the combination of increased ALT/AST and TBL, such as viral hepatitis A, B, or C; preexisting or acute liver disease; or another drug capable of causing the observed hepatocellular injury
- Neutropenic fever
- ≥ Grade 4 neutropenia or thrombocytopenia > 5 days
- ≥ Grade 3 thrombocytopenia with bleeding
- ≥ Grade 4 vomiting/diarrhea of any duration
- ≥ Grade 3 autoimmune disorder. Examples include, but are not limited to, treatment-emergent myasthenia gravis, toxic thyroiditis, bullous pemphigoid, and Stevens-Johnson Syndrome
- ≥ Grade 3 fatigue ≥ 1 week
- ≥ Grade 3 electrolyte abnormalities that lasts > 72 hours or are symptomatic
- ≥ Grade 3 lipase and amylase if associated with symptoms of pancreatitis
- ≥ Grade 3 AST or ALT elevation lasting ≥ 14 days
- Any other ≥ Grade 3 non-hematologic toxicity that is at least possibly related to the study drug

- Recurrent Grade 3 infusion-related reaction despite pre-medication, or Grade 4 infusion-related reaction on the first occurrence
- Dose delay of > 14 days for the study drug due to an AE

All AEs of the specified grades will be considered DLTs except those that are clearly and incontrovertibly due to disease progression or extraneous causes.

Part 3

All toxicities will be graded using Common Terminology Criteria for Adverse Events (CTCAE) Version 5.0 based on the investigator assessment. The DLT window of observation will be during Cycle 1.

The occurrence of any of the following toxicities during Cycle 1 will be considered a DLT, if assessed by the investigator to be possibly, probably, or definitely related to study treatment administration.

- Grade 4 nonhematologic toxicity (not laboratory).
- Grade 4 hematologic toxicity lasting ≥ 7 days, except thrombocytopenia:
 - Grade 4 thrombocytopenia of any duration
 - Grade 3 thrombocytopenia associated with clinically significant bleeding
- Any nonhematologic AE \geq Grade 3 in severity should be considered a DLT, with the following exceptions: Grade 3 fatigue lasting ≤ 3 days; Grade 3 diarrhea, nausea, or vomiting without use of anti-emetics or anti-diarrheals per standard of care; Grade 3 rash without use of corticosteroids or anti-inflammatory agents per standard of care.
- Any Grade 3 or Grade 4 non-hematologic laboratory value if:
 - Clinically significant medical intervention is required to treat the participant or
 - The abnormality leads to hospitalization, or
 - The abnormality persists for > 1 week.
 - The abnormality results in a drug-induced liver injury (DILI)
 - Exceptions: Clinically nonsignificant, treatable, or reversible laboratory abnormalities including liver function tests, uric acid, etc.
- Febrile neutropenia Grade 3 or Grade 4:
 - Grade 3 is defined as $ANC < 1000/mm^3$ with a single temperature of $> 38.3^\circ C$ ($101^\circ F$) or a sustained temperature of $\geq 38^\circ C$ ($100.4^\circ F$) for more than 1 hour
 - Grade 4 is defined as $ANC < 1000/mm^3$ with a single temperature of $> 38.3^\circ C$ ($101^\circ F$) or a sustained temperature of $\geq 38^\circ C$ ($100.4^\circ F$) for more than 1 hour, with life-threatening consequences and urgent intervention indicated.
- Prolonged delay (> 2 weeks) in initiating Cycle 2 due to treatment-related toxicity.
- Any treatment-related toxicity that causes the participant to discontinue treatment during Cycle 1.
- Missing > 25% of NL-201 doses as a result of drug-related AE(s) during the first cycle.
- Grade 5 toxicity.

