6.2.1.4 Step-Dosing

Pre-clinical studies of NL-201 suggest that symptomatic toxicity of NL-201 in animals peaks with the first dose, such that symptomatic toxicity caused by subsequent doses is attenuated compared to that caused by the first dose. Dose levels that are not tolerated when given as an initial dose become tolerated after giving 1 or more initial step-doses at a reduced (tolerated) dose level, and remain tolerated in subsequent doses. Thus, if a specific dose level is not well tolerated (ie, elicits DLTs in $\geq 33\%$ of patients), it is possible that tolerability can be improved by providing 1 or more reduced doses. Once the target dose is reached, subsequent doses would be given at the expected dose level for that cohort.

If step-dosing is implemented, dosing during the first cycle of step-dosing will be administered on Day 1 and Day 8 for both Schedule A and Schedule B patients, though in subsequent cycles Schedule A patients will resume Q3W dosing while Schedule B patients will continue Day 1+8 dosing.

The Cycle 1 dose used for step-dosing will be calculated as one half of the highest tolerated initial dose (HTID), ie, the highest initial dose at which $< 33\%$ of patients experience DLTs. Subsequent cycles will increase 1 dose level (DL) at a time to the CTD.

Table 10 Step-Dosing Guidance

Steps	Cycle 1				
	D1	D8	C2	C3	C4
1	0.5 x HTID	0.5 x HTID	CTD		
2	0.5 x HTID	0.5 x HTID	HTID + 1 DL	CTD	
3	0.5 x HTID	0.5 x HTID	HTID + 1 DL	HTID + 2 DL	CTD

C = cycle; CTD = cohort target dose; D = day; DL = dose level; HTID = highest tolerated initial dose

The DLT window for each patient during step-dosing will extend to include the cycle in which the patient first receives the CTD. The DLT window for each cohort is highlighted in gray in [Table 10](#).

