9.3 Populations for Analyses

For purposes of analysis, the following populations are defined in [Table 15](#).

Table 15 Populations for Analyses

Population	Description
Safety Evaluable Population	For Parts 1 and 2, all patients who receive any amount of study drug (NL-201) will be considered evaluable for safety regardless of the duration of NL-201 treatment. This population is defined for Part 1, and Part 2. For Parts 3 and 4, all patients who receive any amount of study drug (NL-201 or pembrolizumab) will be considered evaluable for safety regardless of the duration of treatment. This population is defined for Part 1 and Part 3, and Part 2 and Part 4, expansion cohorts. This population will be used to summarize safety parameters.
Efficacy Evaluable Population	For Parts 1 and 2, all patients with measurable disease by RECIST, who receive any amount of study drug (NL-201) or who discontinue study drug early due to disease progression and/or death will be considered evaluable for efficacy. For Parts 3 and 4, all patients with measurable disease by RECIST, who receive any amount of study drug (NL-201 or pembrolizumab) or who discontinue study drug early due to disease progression and/or death will be considered evaluable for efficacy. This population is defined for Part 1 and Part 3, and Part 2 and Part 4.
DLT-Evaluable Population	Patients enrolled into Part 1 or Part 3 who either complete the first 21 days of study or who experience a DLT.

DLT = dose limiting toxicity; RECIST = Response Evaluation Criteria in Solid Tumors

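### Without step-dosing, a DLT for a dose delay of more than 14 days is established only after the DLT window and the 21-day evaluability point, and no rule keeps such a patient out of the DLT-free count meanwhile

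*Combined protocol and SAP*

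**What the plan says.** Two delay criteria are on the DLT lists in Section 6.2.1.3. Part 1 has "Dose delay of > 14 days for the study drug due to an AE". Part 3 has "Prolonged delay (> 2 weeks) in initiating Cycle 2 due to treatment-related toxicity".

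The same section sets the windows. The monotherapy rule reads: "DLT must occur within Cycle 1 (< 21 days from first dose), or prior to completion of 21 days after first administration of NL-201". For Part 3, "The DLT window of observation will be during Cycle 1".

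The mTPI count uses "DLT-evaluable patients as defined by occurrence of DLT or completion of 21 days on study" (Section 6.2.1.1; Section 6.2.1.2 repeats this for Part 3). Table 15 defines the population as "Patients enrolled into Part 1 or Part 3 who either complete the first 21 days of study or who experience a DLT". The MTD is tied to the "probability of a patient experiencing a DLT with NL-201 during Cycle 1". For Part 1, the synopsis places the escalation decision after the evaluable patients have finished Cycle 1 and the DMC has reviewed safety.

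Only step-dosing lengthens the window: "The DLT window for each patient during step-dosing will extend to include the cycle in which the patient first receives the CTD" (Section 6.2.1.4). A Cycle 2 delay can then fall inside it, so this point concerns dosing without step-dosing.

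**The concern.** A delay is known to have exceeded 14 days only once those days have passed. The dose most likely to be delayed after a Cycle 1 toxicity is Cycle 2 Day 1, which is due just as the window closes. The plan therefore lists a DLT that is established after the patient has become evaluable and, in Part 1, possibly after the escalation decision.

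Applied literally, the window and evaluability rules put a patient whose only DLT is such a delay into the count as DLT-free. Any error then goes one way: a toxicity that the protocol calls dose-limiting is left out of the mTPI count and the MTD in a first-in-human study. Sites, the statistician and the DMC could also count the same patient differently, because no rule says what to do with a patient who is on hold at Day 21.

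**Working it through.** **Inputs.** Windows and criteria: Section 6.2.1.3. Cycle length 21 days; Schedule A dosed on Day 1, Schedule B on Days 1 and 8: Section 6.2.1.1. Visit windows of ±3 days for Cycle 2 Day 1 and ±1 day for Day 8: Tables 1 and 2. Matrices: Figures 5 and 6.

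**Reproducing the matrices.** With x DLTs in n patients, the posterior is Beta(1+x, 1+n−x). The action is the interval with the largest posterior probability per unit length among below, within and above target ± ε (0.33 ± 0.05 in Figure 5, 0.30 ± 0.03 in Figure 6). DU applies if P(p > target) > 0.95. The documents do not state that cut-off, so it is an assumption. With it, all 105 cells checked in each figure match (0 to 8 DLTs, n = 2 to 15); a cut-off of 0.90 fails 7 cells in Figure 5 and 9 in Figure 6.

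Example, Figure 5 with n = 3:
- x = 0: below 0.7313/0.28 = 2.61; within 0.1210/0.10 = 1.21; above 0.1478/0.62 = 0.24. Escalate.
- x = 1: below 0.3132/0.28 = 1.12; within 0.1768/0.10 = 1.77; above 0.5100/0.62 = 0.82. Stay.

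**Calendar.** Less than 21 days from first dose means Days 1 to 21 (Day k is k − 1 days elapsed). The first whole day on which a delay exceeds 14 days is the due day + 15.

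| Dose on hold | Due day | First day > 14 days late | Days elapsed |
|---|---|---|---|
| Cycle 2 Day 1, nominal | 22 | 37 | 36 |
| Cycle 2 Day 1, early edge | 19 | 34 | 33 |
| Cycle 2 Day 1, late edge | 25 | 40 | 39 |
| Part 1 Schedule B Day 8, nominal | 8 | 23 | 22 |
| Part 1 Schedule B Day 8, early edge | 7 | 22 | 21 |
| Part 1 Schedule B Day 8, late edge | 9 | 24 | 23 |

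No row is below 21 days elapsed. By clock hours there is one exception: a Day 8 dose treated as due on Day 7 (6 days elapsed) passes 14 × 24 hours at 20 days elapsed, which leaves under one day inside the window. A patient who misses Day 8 and is dosed on Day 22 is exactly 14 days late, which is not a DLT.

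**Who is left after the other criteria.** Most related Grade 3 or higher non-hematologic events are DLTs outright. In Part 3, missing one of two Schedule B doses is 50%, above the 25% missed-dose limit. What remains is mainly holds for Grade 3 anemia, Grade 3 neutropenia without fever, Grade 3 thrombocytopenia without bleeding, leukocytosis and Grade 2 cytokine release syndrome (Table 11), and in Part 3 Grade 2 irAEs, for which both drugs are held (Table 12).

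**Effect of one uncounted event, both figures.** n = 3: 0 is E, 1 is S, 2 is D, 3 is DU. n = 6: 1 is E, 2 is S. Away from a boundary nothing changes: 0/6 and 1/6 are both E.

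**Chance of at least one such patient.** The documents give no rate. Assuming a per-patient probability q, the chance is 1 − (1 − q)^n:

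| q (assumed) | n = 3 | n = 6 |
|---|---|---|
| 0.02 | 5.9% | 11.4% |
| 0.05 | 14.3% | 26.5% |
| 0.10 | 27.1% | 46.9% |

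**The case against.** A reader might infer that the two criteria can never be met and are dead letters. The documents do not support that. Part 3 asks for the toxicity to occur during Cycle 1, and its window text carries no explicit 21-day limit. A criterion worded as a delay in starting Cycle 2 is naturally dated by the toxicity behind it. For Part 1, the summary of changes gives alignment with current practice and FDA comments as the reason for adding the delay criterion, so it was meant to count. The clock-hour case above also rules out an absolute claim. Onset-dating is therefore the better reading. It is still not written down, and it does not stop a patient on hold from becoming evaluable at 21 days.

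Other text helps as well. The DLT limb of Table 15 has no time limit, toxicity is assessed on an ongoing basis, and the DMC decides with all available safety data. Part 1 also has a Cohort Management Plan, and a full SAP is to follow (Section 9.4.1); neither is available here, so the gap is shown only for this document. These points limit the harm. They do not tell the DMC whether the count it starts from includes the patient on hold.

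Rarity is a fair argument. Symptomatic toxicity in animals peaked with the first dose (Section 6.2.1.4), and many holds will be short because blood products are allowed and NL-201 may resume once steroids are at 10 mg/day prednisone or less. Against that, Section 6.2.2.1 permits delays of up to 21 days without medical monitor approval, so holds of 15 to 21 days are foreseen.

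Finally, duration-based DLTs, such as Grade 3 transaminase elevation lasting at least 14 days, can also cross their threshold after Day 21. A fix confined to delays must not imply that those have to be completed inside the window.

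**Conclusion.** The point holds for Parts 1 and 3 without step-dosing. From nominal due days, a delay DLT is established about Day 37 (Day 34 to 40), or about Day 23 for a held Part 1 Schedule B Day 8 dose. Both fall after the window and after the 21-day evaluability point. On a literal reading the patient is counted as DLT-free, and escalation may be decided before the DLT can be known.

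It would be wrong to conclude that the MTD will be set too high. The number of patients whose only DLT is a delay cannot be derived from the documents and may be zero. One such patient changes the matrix action only at a boundary, and the DMC can override the matrix. The percentages above rest on assumed rates. What is established is a conflict between the DLT list and the counting rules of a primary endpoint, with a possible error in the unsafe direction. It should be fixed because the remedy is cheap.

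**What to change.** Add to Sections 6.2.1.1 to 6.2.1.3 and Table 15, leaving the toxicity lists and matrices unchanged:

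1. *A delay DLT counts toward the DLT window if the AE that caused the delay (in Part 3, a treatment-related toxicity) began in Cycle 1 or was present at the Cycle 2 Day 1 pre-dose check, even if the > 14-day threshold is passed after Day 21.*
2. *A patient whose dose is on hold for such an AE at the end of Cycle 1 or at the Cycle 2 Day 1 check is pending and is not counted as DLT-free in the mTPI until dosing resumes, the delay exceeds 14 days (DLT), or the patient discontinues. A patient who discontinues while on hold for progression or an unrelated AE is replaced per 4.1.3; one who discontinues because of the causal AE is counted as a DLT.*
3. *Nothing here requires duration-based DLT criteria to be completed inside the window.*

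The Cycle 2 Day 1 check has to be included because Schedule A has no scheduled hematology between Day 8 and that visit, so many cytopenias would first be seen there. Section 4.1.3 does not cover a patient who withdraws consent while on hold; the sponsor should say how that patient is handled.

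The cost is waiting time at that dose level: 37 − 21 = 16 days, up to 40 − 21 = 19 at the late edge of the visit window. For a held Part 1 Schedule B Day 8 dose it is 23 − 21 = 2 days, up to 24 − 21 = 3. It arises only when such a patient exists; a cohort with no patient on hold proceeds as now.
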